7.2.3.2 ATRA Administration

Patients should be instructed to:

- Take their ATRA twice daily, split into two equal doses for the requisite dosing duration
- Take their ATRA doses during or immediately after a meal, at about the same time each day
- Swallow their ATRA capsules whole, with a glass of water
- Take their second dose of ATRA approximately 12 hours after their first dose

7.2.4 Missed Doses

Patients who miss more than 2 consecutive doses may be removed from the study at the discretion of the Sponsor.

7.2.4.1 Missed IMG-7289 Doses

Patients who do not take their IMG-7289 dose at the usual required time should take it immediately upon noting that it was not taken; the patient should not take the dose more than 12 hours after the usual dosing time. If a patient misses a dose, they should not take two doses the following day, but should notify their study coordinator and continue with their normal daily dose the following day.

7.2.4.2 Missed ATRA Doses

Patients who do not take their ATRA dose at the usual required time should take it immediately upon noting that it was not taken; however, if it is within 3 hours of their next scheduled dose time, the patient should not take the dose. If a patient misses a dose, they should not take double the dose at the next dosing time, but should notify their study coordinator and continue with their twice daily dosing the following day.

8 DATA SAFETY MONITORING COMMITTEE (DSMC) REVIEWS AND MANAGEMENT OF STUDY TOXICITIES

8.1 Data Safety Monitoring Committee (DSMC) Reviews

Safety will be monitored throughout the study in accordance with a Data Safety Monitoring Plan (DSMP) by a DSMC constituted by, at a minimum: the Imago BioSciences Principal Medical Monitor, a Principal Investigator and an Independent designee, an AML clinical trials specialist with extensive clinical experience. To ensure a quorum of 3 members at all meetings, an alternate DSMC member will also routinely attend Safety Reviews, and participate when needed.

During all phases, the DSMC will review safety parameters, pharmacodynamic (PD) markers and pharmacokinetic (PK) parameters to form conclusions around the safety and pharmacodynamic effect of differing doses, treatment regimens and dosing durations. DSMC reviews are critical, as neither a new dose-finding sub-cohort, nor a duration-finding cohort may commence without DSMC review and recommendation to do so. The DSMC will assess: the safety of each dose and dosing duration, with and without ATRA. The DSMC will also assess: any clinically significant biochemistry trends; the impact of each dose on normal myeloid haematopoiesis; the PD impact of each dose on malignant cells, and whether further cohorts/sub-cohorts in each respective phase are appropriate.

Data from each cohort/sub-cohort will be reviewed by the DSMC after a minimum of 3 patients in a cohort/sub-cohort have completed Cycle 1 and prior to dosing the next cohort/sub-cohort. Safety data to be evaluated, may include: clinical laboratory results, ECGs [ECGs required in the first 9 patients only as there have been no non-clinical cardiovascular findings; if clinically meaningful trends in ECGs are noted, then the DSMC will make a recommendation as to the appropriate action to be taken (i.e., cardiologist consult, additional ECG requirements, etc.); physical examination and vital sign measurements; and AEs/DLTs/Medical Events of Interest (MEOIs). A combination of PD and PK markers will be evaluated, as available, and may include: peripheral white blood cell count; peripheral blast count; reticulocyte count; platelet count; bone marrow blast count; expected changes in immunophenotype; changes in VAF, changes in cytokine profiles; and, changes in PSA (males only). These metrics will be evaluated in the context of PK parameters such as changes in

the clearance of IMG-7289 (with and without ATRA) based on drug concentrations at C_{min} , C_{max} and AUC, as available.

The DSMC is responsible for providing recommendations regarding the conduct of the study and guidance to Investigators to ensure the safety and well-being of all participating patients.

To avoid repetition in this section, additional DSMC responsibilities are detailed below:

- Rest period duration (see Section 9.10, Extended Rest Period):
 - During the initially allowed IMG-7289 treatment cycles, the rest period will remain at 7 days in duration, unless assessment is made by the DSMC that there is no clear indication of the restoration of normal haematopoiesis in the 7 day period or analysis of the IMG-7289 PK parameters in earlier sub-cohorts suggest the rest period duration requires adjusting. Consideration of adjustments to the rest period duration will be based on an assessment that either a specific patient or an entire cohort could benefit from an extended rest period.
 - During the additional cycle period, the rest period may be extended from the 7 day standard to a maximum of 56 days, but only after: 1) the patient has received a minimum of 28 IMG-7289 doses; and, 2) consultation with or recommendation by the DSMC. Such recommendation may be made for a variety of reasons including evidence of tumour reduction, marked hypocellularity in the marrow consistent with myelosuppression, or to enable the return of normal haematopoiesis.
- Cohort/sub-cohort progression: In both the dose-finding and duration-finding phases, more than one pathway is available for cohort progression. In these instances, determination will be made by the DSMC on the most appropriate path for progression. Additionally, as DSMC review of data continues throughout the study, the DSMC may recommend a different cohort progression than is currently outlined in the protocol.
- Doses for use in a cohort/sub-cohort:
 - The DSMC will determine the IMG-7289 dose(s) for use in combination therapy cohorts/sub-cohorts and any duration-finding cohorts. The DSMC may determine (in the presence or absence of DLTs) that use of an IMG-7289 dose not pre-specified in the protocol is appropriate; for example, that a dose-finding sub-cohort of 1 mg/kg/d be studied were the dose of .75 mg/kg/d assessed as potentially too low and 1.5 mg/kg/d potentially too high.
 - As DSMC review continues throughout the study, the DSMC may recommend reducing the ATRA dose and/or adjusting the ATRA dosing duration.
- Transition of patients to a different dose, treatment regimen or dosing duration: Importantly, if a specific dose, treatment regimen or dosing duration is found to be associated with greater therapeutic benefit, patients who have *fully completed* their initially allowed cycles and are receiving a different dose, treatment regimen (i.e., IMG-7289 alone *versus* combination therapy) or dosing duration will be transitioned to the more optimal

dose, treatment regimen or dosing duration at the start of the next cycle. Such transition may occur more than once, as different doses, treatment regimens and dosing durations continue to be evaluated.

DSMC responsibilities will remain in effect until the study has ended.

DSMC reviews during the IMG-7289 alone component of the dose-finding phase are detailed below.

The DSMC will assess the safety of each sentinel patient before the remainder of the sub-cohort is treated. Each dose sub-cohort will be separated by approximately one week to allow for completion and analysis of appropriate safety assessments required for provision to the DSMC. Dose escalation (see Section 7.2.2.1) will proceed in sub-cohorts (i.e., Sub-cohort 1b, 1c) provided that:

1. A minimum of 3 patients from the previous sub-cohort have completed Cycle 1, both the applicable dosing and rest periods
2. The number of patients who experience DLT is within the guidelines (see Section 8.2.2)
3. DSMC review of the previous cohort has determined that:
 - a. The dose administered appears safe
 - b. Further dose escalation is appropriate

There are two potential dose-escalation pathways for Sub-cohort 1d: 6 and 10 mg/kg/d. The dose to be administered in Sub-cohort 1d will be determined at the discretion of the DSMC. Therefore, upon Cycle 1 completion of a minimum of 3 patients in Sub-cohort 1c, the DSMC will assess the safety and pharmacodynamic effects of the earlier sub-cohorts, and reach consensus on:

1. Whether dose escalation should proceed at all, and if so...
2. Whether the appropriate escalation for Sub-cohort 1d is a doubling or a tripling of the 3 mg/kg/d dose administered in Sub-cohort 1c.

Post DSMC confirmation that no further dose escalation is anticipated, the combination therapy cohort will be enrolled.

DSMC reviews during the IMG-7289 in combination with ATRA component of the dose-finding phase are detailed below.

Combination therapy (see Section 7.2.2.1) will proceed in sub-cohorts (i.e., Sub-cohort 1w, 1v, etc.) provided that:

1. A minimum of 3 patients from the previous sub-cohort have completed Cycle 1, both the applicable dosing and rest periods
2. The number of patients who experience DLT is within the guidelines (Section 8.2.2)
3. DSMC review of the previous sub-cohort has determined that:
 - a. The doses administered in combination appear safe
 - b. Further combination therapy is appropriate

Upon DSMC confirmation that no further dose-finding sub-cohorts are anticipated, the DSMC will also make a determination of whether it is safe to extend the dosing duration, to determine whether longer durations are associated with greater therapeutic benefit. The study will then progress to assess the effect of IMG-7289 dosing duration.

DSMC reviews during the duration-finding phase are detailed below.

During the duration-finding phase, the DSMC will assess whether the longer duration of IMG-7289 dosing, with and without ATRA, at the D_p is safe and associated with greater therapeutic benefit using a combination of PD and PK markers. Each duration cohort will be separated by approximately one week to allow for completion and analysis of appropriate safety assessments required for provision to the DSMC.

There are two potential duration-extension pathways for the duration-finding cohorts: duration extension with IMG-7289 alone, or IMG-7289 administered in combination with ATRA. Therefore, prior to opening a duration-finding cohort, the DSMC will assess the safety and pharmacodynamic effects of the earlier sub-cohorts, and reach consensus on:

1. Whether it appears safe to extend the duration of IMG-7289 dosing
2. Whether there appears to be greater therapeutic benefit with IMG-7289 dosed in combination with ATRA.

Based on the above assessments, one of the duration-finding cohorts will commence.

The duration of dosing (see Section 7.2.2.3) will be extended in subsequent cohorts provided that:

1. A minimum of 3 patients in the previous cohort have completed Cycle 1, both the applicable dosing and rest periods
2. The number of patients who experience DLT is within the guidelines (see Section 8.2.2)
3. DSMC review of the previous cohort has determined that:
 - a. The duration of dosing appears safe
 - b. Further duration extension is appropriate

Throughout all phases of the study, if it appears that either a maximally tolerated dose (MTD) or maximally tolerated duration (MTD_d) is reached (see Section 8.2.3), the DSMC will convene to evaluate further dose escalation, combination therapy and/or extended dosing duration.

8.2 Management of Study Toxicities

Adverse event intensity will be evaluated using the National Cancer Institute (NCI) Common Terminology Criteria for Adverse Events (CTCAE) version 4.03, published 14 June 2010.

Dose-limiting toxicity and dose escalation and duration extension decision rules are defined in Sections 8.2.1 and 8.2.2 below. Expected IMG-7289 toxicities based on non-clinical studies are reported in the latest available edition of the Investigator's Brochure. Expected ATRA toxicities are reported in the Product Information (PI) document.

8.2.1 IMG-7289 Toxicity Definitions

Haematologic Toxicity: Haematologic values outside of the normal reference range are inherent features of AML and MDS, and are expected effects of many therapeutic attempts to manage these diseases. These effects will not be considered DLTs.

Both genetic knockdown (KD) of LSD1 mRNA and pharmacologic inhibition of LSD1 show that the loss of LSD1 activity arrests the production of mature red cells, platelets and granulocytes while over-producing monocytes (Sprussel *et al.*, 2012; Kerenyi *et al.*, 2013). Production of cells of lymphoid lineage, B and T cells is unimpaired indicating that LSD1 has very cell-specific functions and its inhibition also has very specific effects. LSD1 inhibition in AML cells causes the induction of monocytic differentiation markers, as well as a reduction of self-renewal potential of leukaemic cells, eventually resulting in apoptosis of treated cells. Thus, the anaemia, thrombocytopenia, neutropenia and monocytosis attending LSD1 inhibition, as observed in animals treated with IMG-7289, reflect primary pharmacodynamic effects. The kinetics of anaemia, thrombocytopenia, and neutropenia following complete LSD1 inhibition are a function of the lifespan of the individually affected cell types. Over the course of LSD1 inhibition, platelet and neutrophil counts are the most affected, reflecting their short mean lifespans of approximately seven and twelve days, respectively. Recovery of peripheral counts is reversible, rapid, and temporarily overshoots baseline values. At lower doses, the effects on haematopoiesis are much less pronounced suggesting that a modicum of residual LSD1 activity is sufficient to support some blood cell formation. Thus, both the duration of LSD1 inhibition as well as the degree of inhibition are critical to the pharmacodynamic effects on myeloid lineages.

The intended dosing plan for high risk AML/MDS patients is predicated on the supposition that LSD1 must be maximally inhibited to achieve the greatest therapeutic benefit. The concentrations of LSD1 inhibitors such as IMG-7289 (free base) used to achieve maximal effects on growth, differentiation and apoptosis *in vitro* with primary patient-derived AML cells as well as AML cell lines are similar to concentrations that *in vivo* inhibit red cell, platelet and granulocyte production. It is therefore expected that high risk AML/MDS patients will require treatment at doses sufficient to induce profound thrombocytopenia and neutropenia. These drug-induced but reversible cytopenias can be managed clinically as needed with platelet and red cell transfusions as well as broad-spectrum antibiotics in the case of febrile neutropenia, as are already standard practices in the routine management of AML/MDS patients receiving intensive SOC chemotherapy.

The effects of IMG-7289 on normal myeloid haematopoiesis observed in non-clinical studies are expected in humans; these are pharmacodynamic effects of LSD1 inhibition by IMG-7289, thus are not regarded as adverse. These events, with the exceptions noted below, will not be considered DLTs.

Dose Limiting Toxicity (DLT): DLT is defined as any one of the following AEs that occurs during the first cycle of therapy and is considered by the Investigator to be possibly, probably or definitely related to IMG-7289.

- A clinically significant bleeding event;
- Any Grade 4 or 5 non-haematologic adverse event;

- Any Grade 3 non-haematologic adverse event with failure to recover to Grade 1 within 7 days of drug cessation, with the following exceptions:
 - ≥ Grade 3 nausea, vomiting or diarrhoea that responds to standard medical care
 - ≥ Grade 3 aesthenia lasting less than 14 days
- Any Grade 3 electrolyte abnormality unrelated to the underlying malignancy and persisting greater than 24 hours.

Patients who experience a dose limiting toxicity (DLT) will have their dose adjusted downward if the Medical Monitor and Principal Investigator deem it safe for the patient to continue on IMG-7289. To ensure a minimum of 3 Cycle 1 completers, and contingent on the number of prior DLTs within the sub-cohort/cohort, such patients may be replaced.

Any patient that experiences a DLT that results in discontinuation of IMG-7289 therapy may begin alternative therapy after a one week washout period and if their physician deems this safe and appropriate regarding the resolution of the DLT.

Please consult the Medical Monitor for IMG-7289 dose modifications for the management of clinically significant changes in platelets, neutrophil counts, or other haematologic parameters.

Expected toxicities based on non-clinical studies with IMG-7289 are reported in the latest edition of the Investigator's Brochure.

CCI

CCI

Additionally, the DSMC may review safety data and, even in the absence of 2 DLTs, deem that the safe dose has been exceeded. Were this to occur, dose escalation would cease.

Table 5: IMG-7289 Dose Limiting Toxicity and Escalation Decision*

Patients with DLT at a Given Dose	Escalation Decision Rules
0-1 out of 3	Open subsequent sub-cohort/next dose
2 out of 3	Dose escalation will be stopped

*The above instruction applies in kind for combination therapy and duration extension decision making.

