11.2 Adverse Events

The Investigator is responsible for monitoring the safety of patients who have enrolled in the study and for accurately documenting and reporting information as described in this section. Patients will be instructed to report to the Investigator any AE that they experience. Investigators will ask about the occurrence of AEs at each visit. Investigators are required to document all AEs occurring during the clinical study, commencing with the first dose of IMG-7289 through to the End of Study Visit (scheduled at 28 days post last IMG-7289 dose). Adverse event recording will continue for patients

who discontinue study treatment early but remain in follow-up, until their End of Treatment, Pre-End of Study and End of Study Visits have been completed.

Note: Any medical event which occurs from the time of Informed Consent but prior to dosing with IMG-7289 must still be documented in the patient's medical notes and will be recorded on the appropriate medical history CRF pages.

Adverse events will be recorded on designated CRF pages. Each AE is to be characterised (i.e., verbatim term) and information provided regarding its seriousness, start and stop dates, intensity, outcome, and causal relationship with the study drug.

An AE is any undesirable physical, psychological or behavioral effect experienced by a patient during participation in an investigational study, in conjunction with the use of the drug or biologic, whether or not product-related. This includes any untoward signs or symptoms experienced by the patient from the time of first dose with IMG-7289 until completion of the study.

Adverse events may include, but are not limited to:

- Subjective or objective symptoms spontaneously offered by the patient and/or observed by the Investigator or medical staff
- Findings at physical examinations
- Laboratory abnormalities of clinical significance

Progression of underlying malignancy is not reported as an AE if it is consistent with the suspected progression of the underlying cancer. Clinical symptoms of progression may be reported as AEs if the symptom cannot be determined as exclusively due to the progression of the underlying malignancy or does not fit the expected pattern of progression for the disease under study. If there is any uncertainty about an AE being due to only the disease under study, it should be reported as an AE.

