11.2.2 Adverse Event Relatedness

The Investigator will make a judgment regarding whether or not, in his/her opinion, the AE was related to study drug. The Investigator will also evaluate any changes in laboratory values, make a determination as to whether the change is clinically significant, and whether or not the change(s) were related to study drug. However, even if the Investigator feels there is no relationship to the study drug, the AE or clinically significant laboratory abnormality MUST be recorded on the CRF. Below are guidelines for relationship assessment:

- Unrelated: There was no relationship of the adverse event to the use of the drug or biologic. This may include, but is not limited, to the adverse experience being an expected outcome of a previously existing or concurrent disease, concomitant medication or procedure the subject experienced during their treatment period.
- Remote/Unlikely: Adverse events which are judged probably not related to the drug or biologic.
- Possible: There was no clear relationship of the adverse event to the use of the drug or biologic; however, one cannot definitively conclude that there was no relationship.

- Probable: While a clear relationship to the drug or biologic cannot be established, the event is associated with an expected adverse event (per the current Investigator Brochure or DSMC findings) or there is no other medical condition or intervention which would explain the occurrence of such an experience.
- Definite: The relationship of the use of the drug or biologic to the experience is considered definitively established.

If a causal relationship is considered probable, possible, or definite by the Investigator, the AE is considered to be “related” for purposes of regulatory reporting. If a causal relationship is considered remote/unlikely or unrelated, the AE is considered “unrelated” for purposes of regulatory reporting.

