11.2.3 Serious Adverse Events

Serious adverse events will be reportable from the time the time of first dose through the End of Study Visit (scheduled for approximately 28 days post last IMG-7289 dose) **or** until the Investigator and Imago BioSciences determine that follow-up is no longer necessary. Serious adverse events that are suspected to be drug related will be reported even if they occur when the patient is no longer on the study.

An SAE is any AE that results in any of the following outcomes:

- Death[‡]
- Life-threatening experience
- Required or prolonged inpatient hospitalisation[‡]
- Persistent or significant disability/incapacity
- Congenital anomaly
- Important medical events that, based upon appropriate medical judgment, may jeopardise the patient and may require medical or surgical intervention to prevent one of the outcomes listed above.

Life-threatening experience. Any adverse event that places the patient, in the view of the reporter, at immediate risk of death from the adverse event as it occurred, i.e., does not include an adverse event that had it occurred in a more severe form, might have caused death.

Required or prolonged inpatient hospitalisation. The adverse event resulted in an initial inpatient hospitalisation or prolonged an existing hospitalisation of the patient. If a patient is hospitalised as part of the clinical use of the product, a period of normal hospitalisation will be outlined in the protocol or by the judgment of the Investigator. Hospitalisations longer than this period will be prolonged hospitalisations.

Persistent or significant disability/incapacity. An adverse event that resulted in a substantial disruption of a person’s ability to conduct normal life functions.

Congenital Anomaly. The exposure of the patient to the drug or biologic during pregnancy that is

judged to have resulted in the congenital anomaly/birth defect.

Important medical events. Adverse events that may not result in death, be life-threatening, or require hospitalisation may be considered a serious adverse event when, based upon appropriate medical judgment, may jeopardise the patient or subject and may require medical or surgical intervention to prevent one of the outcomes listed above. Important medical events or interventions may be considered an SAE based upon medical judgment of the Investigator.

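### Section 8.2.1 and the synopsis class drug-induced falls in blood counts as not adverse, while Section 11.2 requires clinically significant ones to be recorded, so AE and SAE tables and 24-hour SAE reporting can miss them

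*Protocol*

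**What the plan says.** **Toxicity definitions.** Protocol Section 8.2.1, repeated in the synopsis, says of the expected effects on normal myeloid haematopoiesis that "these are pharmacodynamic effects of LSD1 inhibition by IMG-7289, thus are not regarded as adverse". The next sentence deals with DLTs separately: "These events, with the exceptions noted below, will not be considered DLTs". The same section expects that high-risk patients "will require treatment at doses sufficient to induce profound thrombocytopenia and neutropenia" and that the cytopenias "can be managed clinically as needed with platelet and red cell transfusions".

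**Adverse event rules.** Protocol Section 11.2 includes among possible AEs "Laboratory abnormalities of clinical significance". It treats a finding as clinically significant when it matters medically and may change care. Abnormalities present before treatment are not AEs unless they recur after recovery or show a clinically significant exacerbation. Section 11.2.2 adds that, even when the investigator sees no link to the drug, "the AE or clinically significant laboratory abnormality MUST be recorded on the CRF". Section 11.2.3 makes AE status the entry condition for seriousness: "An SAE is any AE that results in any of the following outcomes". Section 11.2.4 sets a 24-hour limit for reporting SAEs, whatever their relation to the drug.

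**Analysis.** Protocol Section 12.4.1 and SAP Section III.A place AEs and SAEs within the primary safety endpoint. SAP Section IX.A builds its tables from the AEs entered on the eCRF.

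**The concern.** The same event gets two classifications. A platelet fall that is caused by the drug and leads to transfusion is a pharmacodynamic effect and not adverse under Section 8.2.1. It is a clinically significant laboratory abnormality under Section 11.2. The protocol does not say which section prevails, and Section 11.2 does not refer back to 8.2.1.

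Two things are at stake. The first is the AE and SAE part of the primary safety endpoint: if sites read the text differently, haematologic event rates by cohort depend partly on which site enrolled whom. The second is expedited reporting: a hospitalisation for a drug-induced cytopenia could stay off the 24-hour route because the underlying event was never classed as an AE.

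**Working it through.** The documents state no figure on this point, so the check sets the texts side by side.

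1. **Is the Section 8.2.1 statement only a DLT rule?** Not as worded. Section 8.2.1 opens by excluding blood values inherent to AML and MDS from DLTs, and says nothing there about whether they are adverse. For drug effects it makes two statements: they are not adverse, and, in a separate sentence with its own exceptions, they are not DLTs. If the first meant only the second, it would be redundant.

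2. **Does Section 11.2 cover the same events?** Yes. Section 8.2.1 anticipates transfusion for these cytopenias, and antibiotics if febrile neutropenia occurs. It also sends clinically significant changes in platelets and neutrophils to the Medical Monitor for decisions on dose. Events that lead to such actions meet Section 11.2's test of medical relevance with a possible change in care.

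3. **Does any exemption in Section 11.2 settle the conflict?** There are two relevant ones. Progression of the malignancy is exempt, but a drug-induced fall in normal blood production is not progression. Pre-existing abnormalities are also exempt, and this matters because many patients enter with abnormal counts. An unchanged low count is therefore not an AE under either section. A clinically significant exacerbation is an AE under Section 11.2, and that is where the two sections part.

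4. **What follows for SAEs?** Section 11.2.3 defines an SAE as an AE with a serious outcome. An event classed as not adverse fails the entry condition, so the 24-hour rule in Section 11.2.4 is not reached.

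5. **Does the SAP repair it?** Not in the text that can be read. Section IX.A tabulates what sites entered, and no rule derives AEs from laboratory data.

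6. **What still captures the events?**
   - SAP Section IX.B: laboratory shift tables by CTCAE grade and by clinical significance.
   - SAP Section X.D: transfusions.
   - SAP Section X.B: dose changes, interruptions and withdrawals, with reasons.
   - Protocol Section 8.1: the DSMC may review laboratory results, platelets, white cells and reticulocytes directly.
   - Protocol synopsis: febrile neutropenia admissions are assessed.
   - Protocol Section 8.2.1: drug-related, clinically significant bleeding in the first cycle is a DLT.

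   Together these show the counts and much of their management. They do not replace the AE record of seriousness and relatedness, or expedited reporting of cytopenias.

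7. **How sensitive are the tables?** About 8 sites are planned, and a cohort may have as few as 3 patients. In a cohort of 3, one patient's event recorded or omitted moves the incidence by 1/3, about 33 percentage points. This shows how coarse the table is; it does not estimate how often omission would occur.

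**The case against.** The best defence is that Section 8.2.1 is not about recording at all. Section 8.2 introduces it as the place where dose-limiting toxicity is defined, and Section 11.2 tells investigators to document and report events as that section describes. The duty in Section 11.2.2 also covers a clinically significant laboratory abnormality as an alternative to an AE, so it does not hang on the word adverse. On this view a site that enters nothing has misread the protocol.

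Much of that stands. The protocol nowhere tells sites to leave cytopenias out, and a DLT-only intent is plausible. But the text does not state that intent. The duty in 11.2.2 could also be met by a CRF entry that is not an AE entry, whereas the SAP tables and the SAE definition both need an AE.

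Parts of the plan are also unseen: Section 8.2.2 and the SAP adverse-event section contain redactions, and the eCRF completion guidelines that the SAP mentions are not among the documents. Any of these might settle how sites record cytopenias, so actual divergence between sites is possible rather than shown.

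A reader might infer that under-recording would flatten the dose-toxicity relation the DSMC sees. The documents do not support that for blood counts: the DSMC may see them directly, and the escalation rule counts DLTs, whose definition is not in question.

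**Conclusion.** The contradiction is real and should be removed. Its reach is limited to AE and SAE classification, the tables built on it, and the 24-hour SAE route for drug-induced cytopenias. Count data, transfusion summaries, febrile neutropenia admissions and the bleeding DLT are unaffected.

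No numerical size can be given. The documents state neither an expected rate of clinically significant cytopenia nor how sites would divide between the two readings. A reader might infer that recorded incidence could swing from none to all patients. That does not follow, because Section 11.2 itself leaves out unchanged pre-existing abnormalities, so full recording is not what its faithful use would give.

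The conclusion assumes that the redacted text and the eCRF guidelines do not already resolve the matter, and that at least some sites could take the sentence in 8.2.1 at face value.

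**What to change.** Reconcile the two passages. In Section 8.2.1 and in the synopsis, replace the clause that calls these effects not adverse with wording such as: *these effects are not counted as DLTs except as noted below; AE and SAE recording follows Section 11.2, including its rule on pre-existing abnormalities.* Leave the DLT definition and Section 11.2 as they are. The new sentence should not set its own threshold, such as any worsening from baseline, because that would be broader than the clinically significant exacerbation that Section 11.2 requires.

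The cost is one sentence in two places and a matching note to sites on CRF completion. The downside is more AE and SAE entries for cytopenias. Section 3.7 shows that the first four dose-finding sub-cohorts already have pharmacokinetic results, so sites should also be asked to check earlier entries against Section 11.2. Otherwise a change in recording practice would coincide with the change of cohort.
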